4.5 SECONDARY ENDPOINTS

The secondary endpoints will examine the effects of iCO versus placebo on the following outcomes:

- Lung Injury Score (LIS) on days 1-5, and 7
- $\text{PaO}_2/\text{FiO}_2$ ratio on days 1-5, and 7
- Oxygenation Index (OI) on days 1-5, and 7
- Dead Space Fraction (Vd/Vt) on days 1-3, and 7
- Sequential Organ Failure Assessment (SOFA) score on days 1-5, 7, 14, 28

Additional secondary endpoints will examine the effects of iCO versus placebo on biomarkers of mitochondrial dysfunction, inflammasome activation, and lipid mediators in patients with ARDS.

- Autophagy markers (eg. LC3B)
- Inflammasome-dependent cytokines (eg. IL-18)
- Lipid mediators (LM) and specialized pro-resolving mediators (SPMs)
- Mitochondrial quality control biomarkers (eg. Pink1, Wipi1)
- Biomarkers of inflammation (eg. IL-6, IL-8, IL-10, IL-1Ra)
- To enhance the biologic analytic power, samples from 12 subjects enrolled in a similar, already completed study will be similarly analyzed for these biomarkers, as well as in more extensive biologic 'omics profiling that will permit more detailed analyses of these pathways in correlation with clinical data.

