10.2 SAMPLE SIZE DETERMINATION

A total of 32 subjects will be enrolled accounting for a 10% of loss of follow up. Sample size is based on 80% power to detect a difference in change from baseline to day 5 (or death whichever comes first) in mtDNA. With 16 subjects in the placebo arm and 16 subjects in the iCO arm, we will have 80% power to detect a 17225 absolute difference in change in mtDNA (copies/ μ l) from baseline to day 5 (or death whichever comes first) between treatment arms, assuming a conservative 14011 standard deviation (SD)¹⁶⁶ (Table 4). We will also have 80% power to detect a 0.98 difference in LIS, 81 mm Hg difference in PaO₂/FiO₂, and a 0.147 difference in Vd/Vt between treatment arms, assuming an SD of 0.8, 66, and 0.12 respectively^{167,168} (Table 5). With 16 patients randomized to iCO (Table 6), there will be a 77% probability of observing at last one AE that has a 10% background rate and a 96% probability of observing at least one AE that has a 20% background rate.

With 16 patients to each arm, we demonstrated differences in proportions with 2-sided 5% alpha (Table 7).

Table 4. Minimal Detectable Difference at 80% Power for Primary Outcome

Endpoint	Expected Mean Change in Placebo Arm	Expected Mean Change in iCO Arm	Standard Deviation	Detectable Absolute Difference (alpha=5%)
Change in mtDNA (copies/ μ l)	13348	-3877	14011	17225

Table 5. Minimal Detectable Difference on Day 7 at 80% Power for Secondary Endpoints

Endpoint	Detectable Absolute Difference on Day 7 (alpha=5%)	Standard Deviation
LIS	0.98	0.8
PaO ₂ /FiO ₂	81	66
OI	12.4	10.097
Vd/Vt	0.147	0.120
Vasopressor free days	5.2	4.2
Ventilator free days	13.7	11.2
ICU free days	12.6	10.3

Table 6. Probability of observing 1 or more events on the iCO arm for different background AE rates.

n	Background AE rate	Probability to detect ≥ 1 AE
16	0.010	0.13
16	0.020	0.25
16	0.035	0.39
16	0.050	0.51
16	0.100	0.77
16	0.150	0.90
16	0.200	0.96

Table 7. Adverse Events: Differences in proportions that can be demonstrated with 16 on each arm, 2-sided 5% alpha.

Placebo Proportion	iCO Proportion	Difference	Power
0.40	0.0191	0.3809	0.80
0.40	0.0042	0.3958	0.85
0.40	0.0000	0.4000	0.90
0.45	0.0459	0.4041	0.80
0.45	0.0293	0.4207	0.85
0.45	0.0103	0.4397	0.90
0.50	0.0762	0.4238	0.80
0.50	0.0580	0.4420	0.85
0.50	0.0370	0.4630	0.90

PASS version16, test for two proportions, unpooled
variance

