10.4.3 ANALYSIS OF THE SECONDARY AND EXPLORATORY ENDPOINTS

LIS, PaO₂/FiO₂, oxygenation index (OI), dead space fraction (Vd/Vt), and SOFA will be analyzed using repeated measures analysis of covariance (ANCOVA) to assess the effects of treatment, time, and the interaction between time and treatment, while incorporating between-patient variation in baseline measurements and important covariates including severity of ARDS (SAS PROC MIXED). Interaction contrasts will include polynomial trends

across time, focusing on a linear trend suggesting improvement and a quadratic trend suggesting that improvement is leveling off. As part of our analysis, we will also include the interaction between treatment and ARDS severity in the model. Because the study is not powered for the interaction between treatment and severity of ARDS, this test will be exploratory. We will also perform post-hoc analyses within each severity group to generate hypotheses for future study. For analysis of secondary endpoints, we will compare biological outcomes between treatment arms using the Mann-Whitney U or t-test for numerical endpoints and either χ^2 or Fisher's exact test for categorical outcomes.

Based on our prior work^{3,169}, the SD of the log-IL-18 is approximately 0.7. With 16 subjects in the placebo arm and 16 in the iCO arm, we will have > 80% power ($\alpha = 0.05$) to detect a difference in IL-18 levels of 0.5 log which corresponds to a 1.65-fold difference in plasma IL-18.

Based on an interim analysis of Cohort 1 in our Phase I trial, we will also have >80% power to detect a difference in a number of LM and SPMs including PGD₂, PGE₂, PGF_{2 α} , TXB₂, RvD2, and Mar1. Briefly, for multivariate statistical analysis, partial least square discriminant analysis (PLS-DA) will be performed as we have done previously¹⁷⁰. As we are testing multiple secondary and exploratory endpoints, a conservative 1% α level (ie. $p < 0.01$) will be used to accept statistical significance.

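### The stated power of more than 80% for IL-18 is wrong as written: 16 per arm gives about 50% at alpha 0.05 and about 25% at the plan's own 0.01 level

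*Combined protocol and SAP*

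**What the plan says.** Section 10.4.3 gives every input for the IL-18 power statement in one place. Citing the investigators' prior work, it says that "the SD of the log-IL-18 is approximately 0.7". It continues "With 16 subjects in the placebo arm and 16 in the iCO arm" and claims more than 80% power at alpha 0.05 "to detect a difference in IL-18 levels of 0.5 log which corresponds to a 1.65-fold difference in plasma IL-18".

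Two further statements in that section bear on the claim:
- The test for biomarkers is unadjusted: "we will compare biological outcomes between treatment arms using the Mann-Whitney U or t-test for numerical endpoints".
- The significance level for this family of endpoints is stricter than 0.05: "As we are testing multiple secondary and exploratory endpoints, a conservative 1" per cent level is adopted, so p must fall below 0.01.

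IL-18 belongs to that family. Section 4.5 lists it among the secondary biomarkers as "Inflammasome-dependent cytokines (eg. IL-18"). No power is stated for IL-18 at 0.01.

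**The concern.** A difference of 0.5 with an SD of 0.7 is about 0.71 SD. Sixteen per arm is a small sample for an effect of that size, so a claim of more than 80% power looks wrong on sight. It also sits badly with Table 5 in Section 10.2. For the same trial at alpha 5%, that table gives the smallest difference detectable with 80% power as 0.98 for Lung Injury Score with SD 0.8, which is 1.225 SD. One sample cannot need about 1.2 SD for 80% power on one endpoint and exceed 80% at 0.71 SD on another under the same kind of test.

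At stake is how informative the IL-18 comparison is. The plan implies that a true 1.65-fold effect would be missed less than 20% of the time. If that is wrong, anyone weighing the inflammasome hypothesis has a mistaken idea of what the trial can show.

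**Working it through.** **Inputs, all from Section 10.4.3:** difference 0.5 log; SD 0.7; n = 16 per arm; alpha 0.05 as stated and 0.01 as the decision level. The log is natural, since exp(0.5) = 1.65, which matches the stated fold difference. Sidedness is not given for IL-18. Two-sided is assumed, in line with Section 10.2 for adverse events ("we demonstrated differences in proportions with 2-sided 5% alpha").

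**Step 1. Standardised difference.** d = 0.5/0.7 = 0.714.

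**Step 2. Noncentrality.** d × √(n/2) = 0.714 × √8 = 2.02.

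**Step 3. Attempt to reproduce the plan's figure (alpha 0.05).**
- Normal approximation: Φ(2.02 − 1.96) = Φ(0.06) = 0.52.
- Exact noncentral t, 30 degrees of freedom: 0.498.

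The stated figure of more than 80% is not reproduced.

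**Step 4. Power at the decision level (alpha 0.01).**
- Normal approximation: Φ(2.02 − 2.576) = 0.29.
- Exact noncentral t: 0.253.

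The chance of missing a true 1.65-fold effect is therefore about 1 − 0.25 = 75%.

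**Step 5. Other readings.**

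| Reading | alpha 0.05 | alpha 0.01 |
|---|---|---|
| Two-sided t, 16 per arm | 0.498 | 0.253 |
| One-sided t, 16 per arm | 0.629 | 0.346 |
| Mann-Whitney, 16 per arm, normal data (20,000 simulations) | 0.47 | 0.23 |
| Two-sided t, 14 per arm | 0.444 | 0.210 |
| Two-sided t, 50 per arm | 0.943 | 0.825 |

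The row for 14 per arm reflects the 10% loss in Section 10.2: 32 × 0.9 = 28.8, or about 14 per arm. No reading with 16 per arm, SD 0.7 and a difference of 0.5 comes near 80%.

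**Step 6. What 80% power would require.**
- Sample size for 0.5 log (exact t): 32 per arm at 0.05 and 48 per arm at 0.01.
- Detectable difference with 16 per arm: 0.72 log (2.05-fold) at 0.05 and 0.90 log (2.45-fold) at 0.01.
- Detectable difference with 14 per arm: 0.77 log (2.16-fold) and 0.97 log (2.63-fold).
- SD that would make the claim true with 16 per arm: about 0.49 at 0.05 and 0.39 at 0.01, against the stated 0.7.

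**Step 7. Precision of the IL-18 comparison.** The confidence half-width is t × 0.7 × √(2/16) = t × 0.2475.
- 95%: 2.042 × 0.2475 = 0.505 log (1.66-fold).
- 99%: 2.750 × 0.2475 = 0.681 log (1.98-fold).

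**The case against.** The strongest case on the other side is about consequence. IL-18 is given only as an example within one of several biomarker families. The sample size rests on mtDNA, and no stopping or go/no-go rule uses IL-18. That stands, and it limits the weight of the point. It does not make the figure right.

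A baseline-adjusted analysis could in principle rescue the claim at 0.05. It would need a baseline-to-outcome correlation of about 0.72. The plan gives no correlation and specifies an unadjusted test for biological outcomes.

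The 12 earlier subjects might be thought to close the gap. Section 4.5 says only that their samples will be analysed similarly, not that they join the randomised comparison. If they did, with 8 treated and 4 placebo added (24 against 20), power would be about 63% at 0.05 and 38% at 0.01. Four of those treated subjects received 100 ppm rather than 200 ppm (Section 3.2.5).

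The mismatch between the 5% basis and the 1% rule is partly a separate matter. Table 5 also uses 5% for secondary endpoints, and the IL-18 sentence states its alpha openly. The claim fails at 5% in any case.

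Three stronger readings are tempting and are not supported:
- **That the sentence was left over from the larger design.** The amendment history records a change from 100 to 32 participants in version 8.0, and the claim would hold at 50 per arm. A carry-over is possible, but the documents do not say so, and the current sentence does state 16 and 16.
- **That a null IL-18 result will be misread.** Nothing in the plan says a non-significant result will be taken as evidence of no effect.
- **That a null result is inconclusive below about 2.45-fold.** That figure is a detectable difference, not an exclusion limit. By Step 7, an observed difference near zero would exclude effects above about 1.66-fold (95%) or 1.98-fold (99%), while a larger observed difference would exclude less. No fixed fold threshold applies.

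**Conclusion.** The power statement is wrong as written. On the plan's own inputs, power for a 1.65-fold difference in IL-18 is about 50% at alpha 0.05 and about 25% at the 0.01 level that governs secondary endpoints, against a claim of more than 80%. With 14 evaluable per arm it is about 44% and 21%.

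These figures assume a two-sided unadjusted t-test, normally distributed log IL-18 with SD 0.7, and equal arms. A one-sided test at 0.05 reaches only about 63%, so the conclusion does not depend on sidedness.

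The consequence is confined to one secondary biomarker. The mtDNA primary analysis and its sample size are unaffected, so this is an error to correct in the text rather than a threat to the trial's main result.

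**What to change.** Replace the IL-18 power sentence in Section 10.4.3 with:

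*With 16 evaluable subjects per arm, SD 0.7 and a two-sided t-test, power is 80% for a 0.72 log (2.05-fold) difference at alpha 0.05 and a 0.90 log (2.45-fold) difference at alpha 0.01; power for 0.5 log is about 50% and 25%. With 14 evaluable per arm the 80%-power differences are 0.77 log (2.16-fold) and 0.97 log (2.63-fold).*

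Add that a non-significant IL-18 result will be interpreted from its confidence interval, with no fixed fold threshold. Make the same change in the separate Statistical Analysis Plan mentioned in Section 10.4.1 if it repeats the sentence.

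The cost is wording only. The sample size, data collection and analysis do not change; the stated power simply becomes less favourable.

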- Inflammasome-dependent cytokines (eg. IL-18)
- Lipid mediators (LM) and specialized pro-resolving mediators (SPMs)
- Mitochondrial quality control biomarkers (eg. Pink1, Wipi1)
- Biomarkers of inflammation (eg. IL-6, IL-8, IL-10, IL-1Ra)
- To enhance the biologic analytic power, samples from 12 subjects enrolled in a similar, already completed study will be similarly analyzed for these biomarkers, as well as in more extensive biologic 'omics profiling that will permit more detailed analyses of these pathways in correlation with clinical data.

Hypothesis: We hypothesize that, compared to placebo, low dose iCO will reduce mitochondrial dysfunction, attenuate inflammasome activation, and promote resolution of inflammation in patients with ARDS. Furthermore, we hypothesize that modulation of these pathways will predict improvements in the clinical outcomes of our Phase II trial.

- **Exploratory Endpoints:**

- Ventilator-free days at day 28
- ICU-free days at day 28
- Hospital-free days at day 60
- Hospital mortality to day 28 and 60

Focused Safety Analysis:

The incidence of elevation in plasma COHb \geq 10% measured on study days 1-3 and pre-specified administration-associated adverse events (**Section 7.1.8**) and serious adverse events (**Section 9.7**).

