Ventilator-free days (VFDs), hospital- and ICU-free days will each be analyzed separately using ANCOVA with treatment arm as the main effect, however we will only be powered to see large changes in these outcomes (**Table 5**). Mortality will be analyzed using Cox regression models for time-to-death with treatment arm as the main covariate, and with important covariates including age in the model. HR and 95% CI for CO relative to placebo will be reported, along with estimated proportion surviving at 28, 60, and 180 days.

We will assess correlations between biomarkers and clinical and lung physiology outcomes including LIS, SOFA, VFDs, as well as 28- and 60-day hospital mortality. We will use multivariable linear regression as the primary model with LIS as the primary outcome variable. Biomarker levels tend to exhibit right skewedness and large outliers, so data will likely require log transformation. Additional predictor variables (such as demographic variables and comorbidities) will be specified *a priori* and interactions between those variables and biomarkers will be included in the model with adjustment for age as an important biological variable.

To evaluate the predictive ability of biomarkers for binary outcomes, we will use two methods. We will use c-statistics obtained from a logistic regression model to evaluate the effect of biomarker measurements on increasing the area under the receiver operating characteristic (ROC) curves. In addition, we will test if including measured biomarkers to models including important covariates results in an improvement in the net reclassification index as we have done previously for mtDNA³.

For secondary and exploratory endpoints, subjects may also be analyzed according to number of study drug doses completed.

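### The planned NRI and c-statistic assessment of biomarkers has no stated optimism correction or validation; in the fitting data, the usual NRI z-test can exceed the plan's 1% level, well beyond it with several biomarkers.

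*Combined protocol and SAP*

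**What the plan says.** Section 10.4.3 plans two methods for the predictive ability of biomarkers on binary outcomes. The first is discrimination: "We will use c-statistics obtained from a logistic regression model to evaluate the effect of biomarker measurements on increasing the area under" the ROC curve. The second is reclassification: "we will test if including measured biomarkers to models including important covariates results in an improvement in the net reclassification index". The text adds that the group has used the NRI this way before, for mtDNA. The binary outcomes named among the clinical correlates are 28- and 60-day hospital mortality.

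The same section sets the error level: "As we are testing multiple secondary and exploratory endpoints, a conservative 1" per cent alpha level, that is p < 0.01.

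On numbers, Section 10.2 states: "A total of 32 subjects will be enrolled accounting for a 10% of loss of follow up". Section 10.1 adds that "samples from 12 subjects enrolled in a similar, already completed study will be similarly analyzed for these biomarkers", so some biomarker work may draw on 32 + 12 = 44 people.

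The text does not say whether the NRI is category-free or uses risk cut-offs, which standard error applies, how many biomarkers enter a model together, or whether there is bootstrap, cross-validated or external validation. Section 10.4.1 (General Approach) refers detailed analysis to the Statistical Analysis Plan. Nothing further on the NRI appears in the text available here.

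**The concern.** When a variable is added to a fitted logistic model, the fitted risks tend to move towards the outcomes of the patients used for fitting, even if the variable is noise. The apparent NRI and the apparent c-statistic gain are therefore positive on average under the null. A z-test that treats the null NRI as centred on zero is then miscalibrated. The bias grows with the number of variables added and shrinks with the number of events, and a trial of 32 patients will have few deaths.

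At stake is how far the biomarker results can be believed. Section 10.1 hypothesises that modulation of the studied pathways will predict clinical improvement. For mortality, a significant NRI at p < 0.01 would be read as strong evidence from a test that does not hold that level.

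**Working it through.** **Sample size.** The documents give no error rate or power for the NRI test, so there is no NRI figure to reproduce. The trial's size does reproduce. Section 10.2 plans 16 patients per arm and 80% power for a difference of 17225 copies/µl in mtDNA change, "assuming a conservative 14011 standard deviation". The standardised difference is 17225/14011 = 1.23, for which a t-test needs 12 per arm. Dividing by 0.864 for the Mann-Whitney test gives 13.9, so 14. Dividing by 0.9 for loss gives 15.6, so 16 per arm. The trial is sized for mtDNA change, not for predicting death.

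**Inputs.** From the documents: n = 32 (or 44) and level 0.01. Assumed, because the documents are silent: mortality about 30% (25-35%), a base model with two covariates of moderate strength (log-odds slope 0.7, apparent c-statistic about 0.72), and biomarkers that are pure noise. At 30%, expected deaths are 0.30 × 32 = 9.6, or 0.30 × 44 = 13.2.

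**Formulas.** Let pu and pd be the proportions of deaths whose fitted risk moves up or down, and qu and qd the same for survivors.

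- NRI = (pu − pd) + (qd − qu)
- Null SE = √[(pu + pd)/deaths + (qu + qd)/survivors]
- The confidence-interval SE also subtracts (pu − pd)² and (qu − qd)² within the two numerators.

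**Hand check.** For a category-free NRI, pu + pd = qu + qd = 1. With 10 deaths and 22 survivors the null SE is √(1/10 + 1/22) = 0.381. The simulated mean NRI from noise is 0.28, 0.60 and 0.84 for one, three and five biomarkers, or 0.73, 1.58 and 2.20 standard errors. If z had unit variance about those centres, it would pass 2.576 with probability about 3%, 16% and 35%. A valid test would be centred at 0.

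**Simulation.** Models with and without the noise biomarkers were fitted and evaluated in the same patients, with 3000-4000 data sets per setting, n = 32, 30% deaths, two base covariates and a two-sided 1% level. The three-category NRI uses assumed cut-offs of 20% and 40%.

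| Noise biomarkers together | Mean c-statistic gain | Category-free, null SE | Category-free, CI SE | Three-category, null SE | Three-category, CI SE | Ordinary likelihood-ratio test |
|---|---|---|---|---|---|---|
| 1 | 0.025 | 2.0% | 4.0% | 0.2% | 0.9% | 1.9% |
| 2 | 0.052 | 6.4% | 10.8% | 1.5% | 4.0% | 2.8% |
| 3 | 0.074 | 12.9% | 20.8% | 2.7% | 6.9% | 3.7% |
| 5 | 0.116 | 30.0% | 41.2% | 9.5% | 18.7% | 7.2% |

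**Sensitivity.**

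- Three or four base covariates, category-free, null SE / CI SE: one biomarker 3.8% / 6.1-6.9%; three 16.0-19.4% / 23.3-26.7%; five 37.1-43.9% / 47.5-54.4%.
- A stronger base model with one biomarker: up to 7.8% / 10.7%.
- Separate runs with 28-32 patients, 25-35% mortality and two real covariates, category-free, null SE: 2-3%, 13-18% and 32-40% for one, three and five.
- With 44 people, category-free, null SE: about 2%, 12% and 28%.
- Three-category NRI with cut-offs 20% and 50%, null SE: 0.2-0.7% for one, 2-4% for three and 10-15% for five.

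**Calibration check.** For one biomarker, a permutation-calibrated NRI rejected in 0.3% of 300 null data sets. The ordinary likelihood-ratio test rejected in 1.5-3.8% across settings, so it too needs calibration at this size.

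**The case against.** The strongest reply is that the inflation depends on choices the plan does not make. The one precedent it cites is a single biomarker, mtDNA. For one biomarker the excess is modest with a category-free NRI, and absent with a three-category NRI and the null standard error. This stands. A reader might infer that the rule passes useless biomarkers at many times 1% whatever is done. The documents do not support that, since it takes a category-free NRI with several biomarkers entered together. The text does speak of biomarkers in the plural and lists five families of them, so joint entry is a natural reading, but it is not a stated one.

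A reader might also infer that the analysis is confined to the 32 trial patients. That is not stated, and the 12 subjects of the completed study may be added. At 44 people the rates fall only slightly.

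A third tempting inference is that the rule will confirm the pathway hypothesis whether or not any biomarker is prognostic. It does not follow. With five noise biomarkers the category-free null-SE rate is 30-44%, and with one it is a few per cent. The NRI is also not the lead analysis: Section 10.4.3 makes linear regression on LIS the primary biomarker model, and mortality is an exploratory endpoint. Only the NRI is described as tested; the c-statistic is used to evaluate. Its upward bias matters for estimation, not for a p-value.

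Finally, the NRI need not be abandoned, since a permutation-calibrated version kept its level. That also stands and is allowed for in the fix.

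**Conclusion.** The concern holds in a limited form. Followed as written, with no correction or validation, the plan yields NRI and c-statistic gains that are biased upward, and the usual NRI z-test is not assured to hold 1%.

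- Category-free NRI: about 2-4% for one noise biomarker in the central case (up to about 11% with a strong base model), 12-27% for three together and 28-54% for five, depending on standard error, covariates and sample size.
- Three-category NRI, null SE: about 0.5%, 3% and 8-15%.

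These figures rest on assumed mortality, covariate number and strength, and cut-offs, none of which the documents give. They also assume evaluation in the fitting data, which is inferred from the absence of any described validation set. If the Statistical Analysis Plan fixes the NRI version and a validation method, the point reduces to checking that choice. It touches exploratory biomarker work only, and is worth correcting because the correction is cheap.

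**What to change.** Amend Section 10.4.3 and the Statistical Analysis Plan as follows.

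1. Base inference on added value on a likelihood-ratio test of each biomarker, added singly to a fixed base model with age and baseline severity, calibrated by permutation or Firth-penalised, at the plan's 1% level. A simple shuffle of the biomarker is exact only if it is unrelated to the base covariates. Where it is related, permute its residuals, which is approximate.
2. Report the c-statistic change, and the NRI if kept, only as bootstrap optimism-corrected descriptive estimates with 95% confidence intervals. Give no asymptotic NRI p-value; a permutation-calibrated one is an acceptable alternative. If the NRI is kept, state its version and cut-offs.
3. List the biomarkers in advance and say whether the 12 subjects of the completed study are included.

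Testing singly does not remove multiplicity. Section 10.1 names eight example markers and Section 10.4.3 six lipid mediators; 14 tests at 1% give 14 × 0.01 = 0.14 expected false positives per outcome if all are null, which should be acknowledged.

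The cost is wording and analysis code, with no new data. The price is smaller apparent gains and less comparability with the group's earlier NRI results. The null rejection rate of the recommended likelihood-ratio tests was not itself simulated here and should be checked when they are programmed.
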